4.5 Toxicity Management

In response to AEs reported by study participants and/or observed upon exam by study staff, the investigator or designee will recommend either continuation or discontinuation of product use consistent with the criteria in Appendix II. Product use also will be discontinued in the event of pregnancy.

Participants who discontinue product use will not routinely be withdrawn from the study. Rather, every effort will be made to complete the safety evaluations scheduled to take place on study Days 7 and 14, and/or as specified in Appendix II.

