6.2 Adverse Experience Reporting Requirements

An AE is defined as any untoward medical occurrence in a clinical research participant administered an investigational product and which does not necessarily have a causal relationship with the investigational product. As such, an AE can be an unfavorable or unintended sign (including an abnormal laboratory finding, for example), symptom or disease temporally associated with the use of an investigational product, whether or not considered related to the product.

Study participants will be provided a 24-hour telephone number and instructed to contact the study clinician to report any AEs they may experience, except for life-threatening events, for which they will be instructed to seek immediate emergency care. Where feasible and medically appropriate, participants will be encouraged to seek medical care where the study clinician is based, and to request that the clinician be paged or otherwise contacted upon their arrival. With appropriate permission of the participant, records from all non-study medical providers related to AEs will be obtained and required data elements will be recorded on study case report forms. All participants reporting an AE will be followed clinically, until the AE resolves (returns to baseline) or stabilizes.

Site staff also will report all AEs that meet SAE reporting requirements according to the procedures set forth in the Study-Specific Procedures Manual and the time frames set forth in the DAIDS SAE Reporting Manual. Specifically, DAIDS-defined "intensive" reporting requirements will be followed for this study.

Active follow-up for safety outcomes (serious and non-serious AEs) in each study participant will end one day after the final application of study product, however all SAEs reported by participants during the study treatment period and/or during the eight-week period following the final application will be reported in accordance with the DAIDS manual. Information on all AEs will be included in reports to the US Food and Drug Administration (FDA), and other applicable government and regulatory authorities. Site staff will report information on all AEs and SAEs to their Institutional Review Board (IRB) in accordance with all applicable regulations and local IRB requirements.

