7.6 Data Analysis

All descriptive and inferential statistical analyses will be performed using SAS and StatXact statistical software. All randomized participants will be included in all analyses. In the text below, the term "treatment group" refers to a given frequency of a particular product, for sexually abstinent and sexually active participants separately. Secondary analyses will be performed that combine cohorts.

When the use of descriptive statistics to assess group characteristics or differences is required, the following methods are to be used: for categorical variables, the number and percent in each category; for continuous variables, the mean, median, standard deviation, quartiles, and range (minimum, maximum). Within-treatment group assessment of the change from the baseline measurement to the final follow-up measurement will be analyzed using McNemar's test (for categorical response variables) or the paired t-test (for continuous response variables). When the use of formal testing to assess differences between the control gel and CS gel arms is required, the following methods are to be used: for binomial response variables, chi-square tests and logistic regression; for continuous variables, t-tests and linear regression.

Control gel and CS gel participants within each cohort will be compared for baseline characteristics including demographics, pelvic examination, colposcopy, and laboratory measurements using descriptive statistics. Due to the small size of each cohort, formal comparisons will not be performed.

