7.6.1 Primary Analyses

The primary aims of the study are to assess the local and systemic toxicity of once and twice daily application of 6% CS gel versus a control gel among HIV-infected women. The control gel provides information regarding signs, symptoms and/or morbidity that may be attributed to normal variation and/or the study procedures or use of applicator rather than the investigational product being studied. Primary data analyses will tabulate the number of primary endpoints — listed in Section 7.2.1 — observed during the study, by study cohort and product assignment within cohorts. All participants who enroll in the study will be included in each tabulation. Individual participants will contribute once to the calculation of event rates.

Additional safety analyses will tabulate the number and type of AEs observed overall and by severity and relationship to product, by cohort and product assignment. AEs that lead to discontinuation of product use and/or study participation will be tabulated separately. The temporal relationship of product application and AE onset, and the duration of symptoms, also will be evaluated. Finally, baseline, Day 7, and Day 14 laboratory measures will be summarized and the change in function, defined as the difference between the baseline and Day 14 measurements, will be described.

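### Laboratory change is defined only from baseline to Day 14, so a sub-Grade 3 shift at Day 7 that reverses drops out of the one paired laboratory measure

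*Protocol*

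**What the plan says.** Section 7.6.1 deals with laboratory safety in one sentence of two parts. First, "baseline, Day 7, and Day 14 laboratory measures will be summarized". Second, "the change in function, defined as the difference between the baseline and Day 14 measurements, will be described". So levels are reported at all three times, but change is fixed as Day 14 minus baseline.

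Section 7.6 gives a general rule for within-group change: "Within-treatment group assessment of the change from the baseline measurement to the final follow-up measurement will be analyzed using McNemar's test" for categorical variables, or by the paired t-test for continuous ones. It names no particular endpoint.

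Section 7.6.2 is more generous to the exploratory endpoints. Change in HIV RNA copies and in Nugent score is taken from baseline to both Day 7 and Day 14.

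Sections 5.4 and 5.5 schedule the same blood tests at Day 7 (allowed Days 5-9) and Day 14 (allowed Days 12-16). Section 4.5 says "Participants who discontinue product use will not routinely be withdrawn from the study", and asks that the Day 7 and Day 14 safety evaluations still be completed.

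The primary tabulation in Section 7.6.1 counts the Section 7.2.1 endpoints "observed during the study, by study cohort and product assignment within cohorts", and "Individual participants will contribute once to the calculation of event rates".

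**The concern.** Systemic toxicity is a primary objective, and the risks text in Section 8 warns that the anticoagulant effect seen in vitro might appear in these women. The change score is the only paired, continuous laboratory measure that the protocol defines and that does not depend on an investigator's judgment of relatedness. It uses only the last scheduled visit.

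A shift seen at Day 7 can be gone by Day 14 for several reasons: it fades despite continued use, it fades after the last application, or the woman has stopped gel in the meantime. In each case her change is about zero. Women taken off gel for any reason stay in the analysis with off-product Day 14 values, which pulls the group change toward zero.

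The document gives no reason why laboratory safety should have a narrower window than the exploratory endpoints. What is at stake is the description of small, reversible laboratory effects in a first study among HIV-infected women.

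**Working it through.** **1. The plan's own figures, and what they depend on.** The gap attaches to no stated figure. The operating characteristics in Section 7.3 reproduce for 12 women at a true rate of 5%:

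- P(0) = 0.95^12 = 0.540, so P(≥1) = 0.460 (stated 0.46).
- P(0 or 1) = 0.540 + 12 × 0.05 × 0.95^11 = 0.540 + 0.341 = 0.882 (stated 88 percent).

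These probabilities are for women who ever have the endpoint on study. At a true rate of 10%, P(≥1) = 1 − 0.9^12 = 0.718, whether or not the finding has healed by Day 14. Counting at the last visit only would give 0.718, 0.460 or 0 if none, half or all such findings had resolved (assumed range). The primary tabulation does not count that way, so it loses nothing.

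**2. What each planned analysis does with a laboratory value raised at Day 7 and normal at Day 14.**

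| Case | Where it appears |
|---|---|
| Grade 3 or higher, judged related | Primary endpoint, any visit (7.2.1, 7.6.1) |
| Any grade, recorded as an adverse experience | Adverse experience tables; primary endpoint if judged related (6.2, 7.2.1, 7.6.1) |
| Below Grade 3, not recorded as an adverse experience | Day 7 level summary only; change score = 0 |

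The third row is the gap.

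**3. Illustration with clotting time (assumed values).** Take 12 women on CS gel. Three have APTT up 10 s at Day 7 and back to baseline at Day 14; nine never change.

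- Defined change (Day 14 minus baseline): 0/12 = 0 s.
- Change to Day 7, or to the worst of the two visits: (3 × 10 + 9 × 0)/12 = +2.5 s.
- Women shifted: 3/12 = 25%, exact (Clopper-Pearson) 95% CI 5.5% to 57.2%.
- Planned Day 7 level summary: with complete data, the difference between two visit means equals the mean of the within-woman differences. The Day 7 mean therefore also stands 2.5 s above the baseline mean.

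The group mean shift can thus be recovered from the planned tables. What cannot be recovered is which women moved, how many, and by how much.

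**4. Illustration of signal lost in a paired comparison (assumed effect).** Suppose the mean shift at Day 7 is 1 SD of the paired differences, with the same SD at both visits. Power of a two-sided 5% paired t-test comes from the noncentral t with n − 1 degrees of freedom and noncentrality δ√n, where δ is the retained shift in SD units. Group sizes are those of the August 2003 letter of amendment.

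| n per gel | All retained at Day 14 (δ = 1, same as Day 7) | Half retained (δ = 0.5) | None retained (δ = 0) |
|---|---|---|---|
| 12 (Cohorts 1, 2) | 0.88 | 0.35 | 0.05 |
| 10 (Cohort 4) | 0.80 | 0.29 | 0.05 |
| 6 (Cohort 3) | 0.51 | 0.17 | 0.05 |

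Section 7.6.1 says only that laboratory change will be described. These are formal test powers only if the general paired rule of Section 7.6 is applied to laboratory values. Otherwise they gauge how much signal the Day 14 score keeps.

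**The case against.** The strongest reply is that the safety analysis does not rest on the change score. This is correct, and it rules out several broader readings.

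- *A reader might infer that exam findings or symptoms present at Day 7 and healed by the last visit are scored as no effect.* The documents do not support this. If judged related, they are primary endpoints at whatever visit they occur. The wording in Section 7.6 that "the change from the baseline measurement to the final follow-up measurement will be analyzed" is a general rule. No exam-change endpoint is assigned to it; pelvic exam and colposcopy appear in that section only in the descriptive baseline comparison.
- *A reader might infer that an effect leading a woman to stop gel vanishes.* It vanishes only from the change score. Appendix II lists genital conditions and no laboratory trigger, and Section 4.5 ties stopping to adverse experiences or pregnancy. Stopping for a clotting change would therefore be an adverse experience, tabulated separately as one leading to discontinuation.
- *A reader might infer that Day 14 is a washed-out measurement.* For an adherent woman it is not. The window opens at Day 12, missed days are made up after Day 13, and active follow-up ends one day after the last application. In the twice-daily cohorts the Day 7 morning dose is itself usually held until after the exam. Day 14 also reflects the fullest exposure, so it is a defensible time point.
- *The Day 7 summaries would already show the mean shift.* They would, as step 3 concedes. They lack only the pairing.
- *Worst-value definitions belong in a SAP.* A SAP that is not shown may add them. But the protocol does not leave this open: it states a definition, and that definition excludes a visit at which the tests are done.

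What survives is a reversed laboratory shift below Grade 3 that no one records as an adverse experience, and the mismatch between Section 7.6 and Section 7.6.2.

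**Conclusion.** The point holds in a narrow form and is minor. The protocol fixes laboratory change at Day 14 although the same tests are done at Day 7, and it treats two exploratory endpoints more fully. A within-woman shift below Grade 3, not recorded as an adverse experience and reversed by Day 14, counts as zero change and is visible only as part of an unpaired Day 7 summary.

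The size depends on how far such shifts reverse, which the documents do not say. Under the assumed example, the defined measure shows 0 s where 3 of 12 women moved by 10 s. With an assumed 1 SD shift in 12 women, paired power is 0.88 if the shift fully persists and 0.05 if none of it does. If laboratory effects persist to Day 14, nothing is lost. No sample-size figure changes, and the primary tabulation stands as written.

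**What to change.** In Section 7.6.1, describe laboratory change from Enrollment to Day 7 and from Enrollment to Day 14. Add change from Enrollment to the worst post-Enrollment value, with shift tables of worst grade by gel within cohort. In Section 7.6, replace the rule based on the last measurement with one that matches Section 7.6.2, so that change is assessed at Day 7 and at Day 14.

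The cost is about two sentences and some extra tables; no new data, visits or participants are needed. The drawback is that the worst of several values drifts upward by chance in both arms, so it must be read against the control gel and never alone. If interim values are included, an arm with more interim visits has more chances of a high value; showing the worst scheduled value as well would reveal this. With 6 to 12 women per gel in a cohort, the shift tables will be sparse and should remain descriptive.

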7.6.2 Secondary Analyses

Participant adherence to the product use regimen will be assessed within treatment group and comparisons will be made between the control gel and CS gel groups combining the cohorts with covariates for frequency of use and sexual activity. Similar analyses will be performed on the endpoints assessing acceptability. These include male and female participants' willingness to use the assigned product during intercourse in the future (as reported via questionnaire on study Day 14), reported positive aspects of using the assigned product, and reported negative aspects of using the assigned product (as reported via questionnaire). In addition, participants' preferences at Enrollment will be compared with acceptability after having used the study gels.

To explore potential effects of product use on cervicovaginal shedding of HIV, change in the number of copies of HIV RNA from baseline to Day 7 and Day 14 will be analyzed within each treatment group. In addition, the change in the number of copies of HIV RNA will be compared between the control gel and CS gel users and for sexually active and sexually abstinent women.

Similarly, to explore potential effects of product use on vaginal flora, change in Nugent scores from baseline to Day 7 and Day 14 will be analyzed within each treatment group. In addition, change in score will be compared between the control gel and CS gel users and for sexually active and sexually abstinent women.

8.0 HUMAN SUBJECTS CONSIDERATIONS

8.1 Ethical Review

This protocol and the sample informed consent forms contained in Appendix II — and any subsequent modifications — will be reviewed and approved by the HPTN Protocol Review Committee and DAIDS Prevention Science Review Committee with respect to scientific content and compliance with applicable research and human subjects regulations.

The protocol, site-specific informed consent form, participant education and recruitment materials, and other requested documents — and any subsequent modifications — also will be reviewed and approved by the ethical review bodies responsible for oversight of research conducted at the study site.

Subsequent to initial review and approval, the responsible local IRBs will review the protocol at least annually. The Investigator will make safety and progress reports to the IRB at least annually, and within three months of study termination or completion. These reports will include the total number of participants enrolled in the study, the number of participants who completed the study, all changes in the research activity, and all unanticipated problems involving risks to human subjects or others.

8.2 Informed Consent

Written informed consent will be obtained from each study participant prior to the initiation of any study procedures. Each study site is responsible for developing study informed consent forms for local use, based on the samples in Appendix II, which describes the purpose of the study, the procedures to be followed, and the risks and benefits of participation, in accordance with all applicable regulations. Participants will be provided with a copy of their informed consent form if they are willing to receive it. Study staff will document the informed consent process as described in the Study-Specific Procedures Manual.

Female participants may experience discomfort when having pelvic exams and/or undergoing phlebotomy for this study. During phlebotomy, they also may feel dizzy or faint, or develop a bruise or swelling where the needle is inserted; there is a very small chance of the participant getting an infection at the site where the blood is drawn.

Male and female participants may become embarrassed, worried, or anxious when receiving HIV and STD counseling. They also may become worried or anxious while waiting for their HIV and STD test results. Study staff will assist participants in dealing with these feelings.

Based on the prior completed Phase I vaginal study of CS gel versus K-Y Jelly, potential risks to female participants associated with use of the study products include vulvar and/or vaginal redness, itching, burning, or pain; abnormal vaginal bleeding; and abdominal pain and tenderness. For male participants, although exposure to the study products should occur rarely, if at all, given instructions to use male condoms during each act of vaginal intercourse while in the study, the prior Phase I penile study of CS gel indicated that mild penile tingling or stinging may occur if men are exposed to CS gel.

CS gel has been shown to have anticoagulant effects *in vitro*. Although no such effects were observed in the prior Phase I study among HIV-uninfected women, it is possible, that such effect could be observed among participants in this study.

Although study sites will make every effort to protect participant privacy and confidentiality, it is possible that participants' involvement in the study could become known to others, and that social harms may result (i.e., because participants could become known as HIV-infected). For example, participants could be treated unfairly or discriminated against, or could have problems being accepted by their families and/or communities.

8.4 Benefits

There may be no direct benefits to participants in this study. However, participants and others may benefit in the future from information learned from this study. Specifically, information learned in this study may lead to the development of a safe and effective vaginal microbicide that prevents HIV infection. In addition, participants will receive HIV/STD counseling and testing as part of the study screening process, as well as CD4+ cell count and HIV viral load measurements, pelvic exams and Pap smears. Participants will be referred to available sources care if needed to follow up on any medical problems identified as part of the study screening and/or follow-up procedures (see also Section 8.5).

8.5 Access to HIV-Related Care

This study will include HIV-infected women who are under the care of a medical professional for HIV management. Such women will continue with their regular source of care while in this study. As part of the study screening and enrollment process, the study may identify HIV-infected men and women who lack HIV-related care. Study staff will refer such persons to available sources of medical and psychosocial care in their community, as well as to any other available research studies for HIV-infected women.

8.6 Incentives

Pending IRB approval, participants will be compensated for their time and effort in this study, and/or be reimbursed for travel to study visits and time away from work. Site-specific reimbursement amounts will be specified in the study informed consent forms.

8.7 Confidentiality

All study-related information will be stored securely at the study site. All participant information will be stored in locked file cabinets in areas with access limited to study staff. All study data collection, process, and administrative forms, colposcopic photographs, laboratory specimens, and other reports will be identified by a coded number only to maintain participant confidentiality. All records that contain names or other personal identifiers, such as locator forms and informed consent forms, will be stored separately from study records identified by code number. All local databases will be secured with password-protected access systems. Forms, lists, logbooks, appointment books, and any other listings that link participant ID numbers to other identifying information will be stored in a separate, locked file in an area with limited access.

Participant's study information will not be released without the written permission of the participant, except as necessary for monitoring by the NIAID and/or its contractors; CONRAD; representatives of the HPTN CORE, SDMC, and/or CL; the US Food and Drug Administration, and/or other government and regulatory authorities.

8.8 Communicable Disease Reporting Requirements

Study staff will comply with all applicable local requirements to report communicable diseases identified among study participants to local health authorities. Participants will be made aware of all reporting requirements during the study informed consent process.

8.9 Study Discontinuation

The study also may be discontinued at any time by NIAID, the HPTN, CONRAD, and/or the US Food and Drug Administration or other government or regulatory authorities.

9.0 LABORATORY SPECIMENS AND BIOHAZARD CONTAINMENT

9.1 Local Laboratory Specimens

The following types of specimens will be collected for processing at the LL:

- urine,
- vaginal swabs for wet mount,
- ecto- and endocervical specimens for Pap smear,
- serum, and
- plasma.

Each study site will adhere to standards of good laboratory practice, the HPTN CL Manual, the Study Specific Procedures Manual, and local standard operating procedures for proper collection, processing, labeling, transport, and storage of specimens to the LL. Specimen collection, testing, and storage at the LL will be documented in accordance with the Study Specific Procedures Manual.

